Obstructive Sleep Apnea (OSA) is a prevalent condition associated with significant morbidity, including hypertension and cardiovascular disease. Continuous positive airway pressure (CPAP) is the first-line treatment, but adherence is notoriously poor, with long-term compliance as low as 10-20%. For patients intolerant to CPAP, surgical options are offered, yet their long-term success rates average only 30%.

Myofunctional therapy (MFT) addresses the functional dimension of OSA by strengthening oropharyngeal muscles to increase airway stability. A meta-analysis has already demonstrated that MFT alone can reduce the AHI by 50% in adults. The rationale for this study is that surgery primarily addresses static anatomical obstructions, while MFT targets the functional deficit of poor neuromuscular tone that surgery alone cannot correct. We hypothesize that a combined, synergistic approach-where surgery provides anatomical relief and MFT enhances dynamic airway stability-will lead to superior treatment outcomes compared to surgery alone.

4. Study Goals and Objectives

- **Goal:** To determine if adding a structured postoperative MFT program to sleep surgery improves treatment outcomes for patients with moderate-to-severe OSA compared to surgery alone.
- **Primary Objective:**
 - To compare the reduction in AHI at 3 and 12 months post-surgery between the OP+MFT and OP-only groups, with success defined as >50% AHI reduction and a final AHI <20 events/hour.
- **Secondary Objectives:**
 - To compare the change in lowest oxygen saturation (LSaO₂) between the groups at 3 and 12 months.
 - To compare the change in the snore index between the groups at 3 and 12 months.

5. Study Design

This is a prospective, single-surgeon, non-randomized controlled study conducted at a single medical center.

- **Research Population:** Adults aged 20-65 with moderate-to-severe OSA (AHI ≥ 15 events/hour) confirmed by PSG.
- **Inclusion Criteria:**
 - Age 20-65 years.
 - Moderate-to-severe OSA (AHI ≥ 15 events/hour)
 - Friedman palate position grade I-II and tonsil size grade III-IV.
 - Patients who refuse or are unable to tolerate CPAP.
- **Exclusion Criteria:**
 - Central or mixed sleep apnea.
 - BMI $> 27 \text{ kg/m}^2$.
 - Severe cardiopulmonary disease or psychiatric illness.
 - Pregnancy or cancer.
 - Significant weight gain during the follow-up period.

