- **Study Duration:** The project was conducted between January 2020 and January 2024. Each participant's follow-up duration is 12 months.

6. Methodology

- **Interventions:**
 - **Surgery:** All patients will undergo surgery performed by the same surgeon, including uvulopalatopharyngoplasty (UPPP) and adjunctive nasal turbinate reduction surgery.
 - **Grouping:** After surgery, enrolled patients will be divided into two groups based on personal willingness: Group A (OP+MFT) or Group B (OP- only).
 - **Myofunctional Therapy (MFT):** Group A patients will begin a 12-week MFT program starting at the third postoperative week. The program includes:
 - Initial Instruction: Two face-to-face training sessions with a speech-language pathologist in the first week.
 - Home Practice: Twice-daily sessions of 15 minutes each, guided by instructional videos.
 - Exercises: Tongue elevation and protrusion drills, soft palate elevation, pharyngeal wall contractions, and nasal breathing retraining.
 - Supervision: Biweekly review sessions with the therapist to ensure correct performance and adherence.
- **Outcome Measures & Procedures:**

- All participants will undergo overnight polysomnography (PSG) at the sleep center at baseline (pre-surgery), and at 3 and 12 months post-surgery.
- Objective data on AHI, LSaO₂, and snore index will be collected.
- **Study Flow Diagram:** [Eligible OSA Patients] -> [Informed Consent] -> [Baseline PSG] -> [Undergo Surgery (UPPP)] -> [Post-op Group Allocation] ---> [Group A: OP+MFT] -> [12-Week MFT Program] ---> [3-Month PSG Follow-up] -> [12-Month PSG Follow-up] -> [Data Analysis] | +--> [Group B: OP-only] -> [Routine Follow-up] -----+

7. Safety Considerations

Participant safety is paramount. MFT is a non-invasive therapy with minimal risk.

- All surgical procedures will be performed by an experienced surgeon, and standard postoperative care protocols will be followed to manage potential complications such as pain or bleeding.
- The intensity of MFT exercises will be introduced gradually to prevent muscle strain.
- During all follow-up visits, researchers will actively monitor and record any adverse events related to either the surgery or the MFT. All adverse events will be reported to the Institutional Review Board (IRB) in accordance with regulations.

8. Data Management and Statistical Analysis

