- **Data Management:** All research data will be de-identified and coded. The data will be entered into a password-protected electronic database accessible only to the research team.
- **Statistical Analysis:**
 - Continuous variables will be compared using paired or unpaired t-tests.
 - Categorical outcomes will be compared using the chi-square test.
 - A p-value of <0.05 will be considered statistically significant.

9. Quality Assurance

To ensure the quality and consistency of the study:

- All surgeries will be performed by a single surgeon to standardize the surgical technique.
- All MFT instruction and supervision will be conducted by the same speech-language pathologist to ensure consistency in the training protocol.

- All PSG data will be scored according to the standardized guidelines of the American Academy of Sleep Medicine.
- The study will be conducted in strict adherence to the IRB-approved protocol and Good Clinical Practice (GCP) guidelines.

10. Expected Outcomes of the Study

This study is expected to demonstrate that the addition of postoperative MFT significantly enhances the efficacy of surgical treatment for OSA. The findings will provide strong evidence for a multimodal treatment strategy, potentially influencing future clinical guidelines for OSA management. This research will advance the understanding of OSA pathophysiology by highlighting the importance of addressing both anatomical and neuromuscular functional deficits.

11. Dissemination of Results and Publication Policy

The results of the study will be submitted for publication in a peer-reviewed international medical journal. Authorship will be determined based on the contributions of each member of the research team, as detailed in the "Authors' contributions" section of the manuscript.

12. Duration of the Project

The total duration of the project is four years, from January 2020 to January 2024.

- Year 1: Patient recruitment, surgical interventions, and early postoperative follow-up.
- Years 2-3: Continued recruitment and completion of all 3-month and 12-month follow-up assessments.
- Year 4: Data compilation, statistical analysis, and manuscript preparation and submission.

13. Problems Anticipated

- **Problem:** The modest sample size may limit statistical power.
 - **Solution:** Future research could be designed as a larger, multi-center trial.
- **Problem:** The 12-month follow-up period does not capture long-term recurrence.

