 - **Solution:** Future studies should extend the follow-up period to three to five years.
- **Problem:** Adherence to MFT was based on self-report, which could introduce bias.

- **Solution:** Future protocols could incorporate digital tools, such as smartphone apps, for more objective adherence monitoring.

14. Project Management

- **Conceptualization & Supervision:** [name], [name]
- **Data Curation:** [name], [name]
- **Formal Analysis & Methodology:** [name], [name], [name]
- **Investigation:** [name]
- **Writing & Editing:** All authors contributed.

15. Ethics

The study protocol has received ethical approval from the Taipei Medical University Joint Institutional Review Board (TMUJIRB No.201912067). All participants will provide written informed consent before enrollment. Participants will be informed of the study's purpose, procedures, potential risks, and benefits, and will be notified that they can withdraw from the study at any time without penalty.

16. Informed Consent Forms

Copies of the IRB-approved Informed Consent Forms (in both English and Traditional Chinese) will be appended to this protocol. The forms will ensure that participants have all the necessary information to make a voluntary and informed decision about their participation.

Part 2: Administrative and Supporting Documents

1. Budget

This research is funded by the Taipei Medical University Shuang Ho Hospital Young Scholar Research Grant W114YSR-03 and Taipei Medical University Newly Recruited Faculty Research Grant, Project No. TMU113-AE1-B04

2. Other Support for the Project

None.

3. Collaboration with other scientists or research institutions

This project involves collaboration between researchers at Taipei Medical University, Shuang Ho Hospital, National Yang Ming Chiao Tung University, and National Tsing Hua University.

4. Curriculum Vitae of Investigators

The CVs of the Principal Investigator and co-investigators are attached.

5. Financing and Insurance

Participants in this study are covered by the clinical trial liability insurance of the conducting institution, Taipei Medical University-Shuang Ho Hospital

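### The 12-month t-tests leave out patients without a 12-month PSG and ignore their 3-month results: some precision is lost, and bias is possible but usually small

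*Combined protocol and SAP*

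**What the plan says.** The primary objective (section 4) is "To compare the reduction in AHI at 3 and 12 months post-surgery between the OP+MFT and OP-only groups", with success defined by a percentage reduction and a final AHI threshold. The secondary objectives compare change in LSaO2 and snore index at the same two visits. Section 6 schedules PSG "at baseline (pre-surgery), and at 3 and 12 months post-surgery".

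Section 8 gives the whole analysis. The rule for AHI, LSaO2 and snore index is "Continuous variables will be compared using paired or unpaired t-tests". Success falls under a second rule, "Categorical outcomes will be compared using the chi-square test", and the significance threshold is p below 0.05. No section contains a longitudinal model, an imputation rule, an analysis-set definition or a rule for a missed PSG.

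Three other statements bear on loss. Section 15 tells participants that "they can withdraw from the study at any time without penalty". Section 5 lists significant weight gain during follow-up as an exclusion, which can remove a patient after the 3-month PSG. Section 6 says "enrolled patients will be divided into two groups based on personal willingness", and only the MFT group has biweekly therapist review.

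**The concern.** A t-test is a two-column method applied to a three-visit outcome. A patient with baseline and 3-month PSGs but no 12-month PSG contributes nothing to the 12-month comparison, although the 3-month value says a good deal about the missing one. Two things are at stake.

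- **Precision.** Section 13 already warns that the modest sample may limit power.
- **Bias.** The groups are self-selected and have different contact with staff, so the reasons for returning at 12 months could differ between them. If return depends on the 3-month result in one group and not in the other, the 12-month completers are no longer comparable, even in the absence of any MFT effect.

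**Working it through.** **Inputs.** The outcomes, visits and tests come from sections 4, 6 and 8. The documents give no sample size, SD, correlation or dropout rate, so there is no planned figure to reproduce and every size below is an illustration. That the t-test is run visit by visit is inferred: a t-test of 12-month reduction has no other way to proceed.

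**1. Precision from the 3-month data alone.** Let d be the share without a 12-month PSG and ρ the within-group correlation of the 3- and 12-month outcomes. With random loss, the large-sample variance of a likelihood-based repeated-measures estimate relative to completers only is 1 − ρ²d. The equivalent gain in completers is 1/(1 − ρ²d) − 1. For example, d = 0.2 and ρ = 0.7 give 1 − 0.49 × 0.2 = 0.902, a gain of 10.9%.

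| d | ρ = 0.5 | ρ = 0.7 | ρ = 0.8 |
|---|---|---|---|
| 10% | 2.6% | 5.2% | 6.8% |
| 20% | 5.3% | 10.9% | 14.7% |
| 30% | 8.1% | 17.2% | 23.8% |

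Take an effect giving 80% power on complete data (two-sided 5%). Completers-only power is 75.7%, 70.7% and 65.0% at 10, 20 and 30% loss. With the 3-month data it is 76.8-78.4%, 72.9-76.5% and 68.3-74.1%.

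**2. Baseline adjustment is a separate gain.** Let s0 be the baseline SD, s the SD at both follow-up visits, and r the correlation of baseline with follow-up. The variance of a change score is s0² + s² − 2·r·s0·s; after baseline adjustment it is s²(1 − r²). With s0 = 18, s = 14, r = 0.5 these are 324 + 196 − 252 = 268 and 196 × 0.75 = 147. This gain has nothing to do with the 3-month visit.

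Once baseline is adjusted for, the relevant correlation is (ρ − r²)/(1 − r²). With ρ = 0.75 it is 0.667 at r = 0.5 and 0.725 at r = 0.3. At 25% loss the 3-month data then add 1/(1 − 0.25 × 0.444) − 1 = 12.5% and 1/(1 − 0.25 × 0.526) − 1 = 15%. At 10% loss they add about 5%.

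**3. Bias.** Assume no true effect, ρ = 0.75 and 25% loss. In OP-only, the log-odds of loss rise by 1 per SD of 3-month AHI; in OP+MFT, loss is random. Numerical integration gives OP-only completers a 3-month mean that is m = 0.213 SD too low (0.091 at 10% loss, 0.253 at 30%). Bias is expressed on the OP+MFT minus OP-only difference in (12-month − baseline) AHI, so a positive value hides an MFT benefit.

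- Change-score t-test: m(ρs − r·s0)
- Baseline-adjusted regression on completers only: approximately m·s(ρ − r²)
- If dependence runs in opposite directions in the two groups, both double.

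| s0, s, r | ρs − r·s0 | Change score: one group / opposite | Completers-only adjusted: one group / opposite |
|---|---|---|---|
| 20, 15, 0.5 | 1.25 | 0.3 / 0.5 | 1.6 / 3.2 |
| 20, 12, 0.5 | −1.00 | −0.2 / −0.4 | 1.3 / 2.6 |
| 18, 14, 0.5 | 1.50 | 0.3 / 0.6 | 1.5 / 3.0 |
| 18, 14, 0.3 | 5.10 | 1.1 / 2.2 | 2.0 / 3.9 |
| 15, 15, 0.3 | 6.75 | 1.4 / 2.9 | 2.1 / 4.2 |

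All entries are events/h. For the last row with opposite dependence, the change-score bias is 2 × 0.091 × 6.75 = 1.2 at 10% loss and 2 × 0.253 × 6.75 = 3.4 at 30%. With random loss m = 0, and with the same dependence in both groups the shifts cancel.

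Simulation with 40 per group agrees. The change-score t-test was biased by −0.5 to +1.5 events/h in most differential-loss settings and by up to 3.0 in one. The repeated-measures estimate stayed within about 0.15 of zero, as expected when loss depends only on observed values.

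**The case against.** The strongest reply is that nothing in the documents shows that patients will be lost. Section 6 has every participant undergo all three PSGs, section 12 schedules completion of the follow-up assessments, and the withdrawal wording is standard consent language. This stands as a limit on size: if nearly everyone returns, the effect is negligible. It is not an answer on method, because a timetable does not say what happens to a patient who misses a visit.

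Three stronger readings are tempting, and the documents support none of them.

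- **That the planned test is biased by 2 to 4 events/h.** Those values belong to baseline-adjusted regression on completers, which the plan does not contain. The objectives are about reduction and change, so the change-score column applies. In simulations with 40 per group, its type I error was 4.6-5.8% under the first two SD settings in the table; under the last it was 6.5% (one group) and 9.6% (opposite).
- **That the bias hides an MFT benefit.** The sign turns on ρs − r·s0, whose inputs are not given, and on who stays away. OP-only patients with poor results might return more often, not less.
- **That the whole precision gain over the t-test comes from the 3-month data.** With the SDs assumed above, much the larger part comes from baseline adjustment.

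It is also fair to say that allocation by willingness is the larger threat, and that a repeated-measures model leaves it untouched.

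**Conclusion.** The point holds as a should-fix matter of moderate size. The planned 12-month t-tests discard usable data whenever a 12-month PSG is missing. Under 10-30% loss and a correlation of 0.5-0.8, the 3-month results are worth about 3-24% more completers. Bias is conditional: it needs return to depend on the 3-month result differently in the two groups. It is then usually about 1 event/h or less for the change-score test and reaches about 3 only under strong, opposite dependence with unfavourable SDs. Its direction cannot be determined from the documents.

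There is one practical consequence. If baseline adjustment is introduced on completers only, the bias under differential loss can be larger than that of the t-test it replaces, so baseline adjustment and the repeated-measures model should be adopted together.

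**What to change.** Replace the t-test sentence in section 8 with:

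> Each continuous outcome (AHI, LSaO2, snore index) is analysed in one mixed model for repeated measures of the 3- and 12-month values, with group, visit, group × visit, baseline value and baseline × visit, unstructured covariance and Kenward-Roger degrees of freedom, including all patients with at least one follow-up PSG. The between-group difference at each visit is reported with its 95% CI. Paired within-group tests are descriptive. As a sensitivity analysis, the between-group difference in change is estimated from a model with baseline, 3- and 12-month values as responses and baseline means left free to differ by group.

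The success endpoint has the same gap, because a chi-square test at 12 months also needs an observed AHI. Analyse it in all patients with any follow-up PSG, for example by multiple imputation of the missing 12-month AHI from the baseline and 3-month values.

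**Cost.** SAP wording and standard software, with no new data. Section 5 describes the study period in the past tense; if outcome data have already been seen, the change should be dated and labelled post hoc.

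**Downsides to state in the plan.** The model assumes that missingness is explained by observed values. Baseline-adjusted and change-score estimates may differ in self-selected groups, which is why the sensitivity analysis leaves baseline means free. Neither estimate removes confounding from allocation by willingness.
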